2.2. Secondary objectives and endpoints

The secondary objectives are:

To evaluate the proportion of patients requiring hospitalization during the study compared to the {Standard of care + placebo} group

- *Rate of patients hospitalized*

To assess the proportion of patients reporting each severity rating on a 7-point ordinal scale during the course of the study compared to the {Standard of care + placebo} group

- *Percentage of patients reporting each severity rating on a 7-point ordinal scale at each study visit (i.e. Not hospitalized, no limitations on activities; Not hospitalized, limitation on activities; Hospitalized, not requiring supplemental oxygen; Hospitalized, requiring supplemental oxygen; Hospitalized, on non-invasive ventilation or high flow oxygen devices; Hospitalized, on invasive mechanical ventilation or ECMO; Death);*

To assess the time to an improvement of one category of the 7-point on an ordinal scale from baseline, compared to the {Standard of care + placebo} groups

- *Change in the ranking on an ordinal scale from baseline to days 7, 14, 21, 28, 48 and at 4 months*

To evaluate and compare the effect of ABX464 on oxygen saturation before hospitalization

- *% change and AUC over time of oxygen saturation measured by daily pulse oximetry before hospitalization*

To evaluate and compare the effect of ABX464 on oxygen saturation level at the end of the study treatment

- *Rate of patients with SpO₂ ≤ 94% and rate of patients with SpO₂ ≤ 92% at Day 28*

To evaluate and compare the effect of ABX464 on immunophenotyping (in selected sites only) and cytokines levels during the study in patients enrolled in both treatment groups.

- *Change from enrolment in inflammatory markers in plasma (i.e. MCP-1, MIP-1 α , G-CSF, IL-1 β , IL-2, IL-6, IL-7, IL-10, IL-17, INF γ and TNF α) and in immune phenotype and assessment of cell-activation markers in PBMCs at D14, D28.*

To evaluate the proportion of patient requiring oxygen supplementation (>3L/min) during the study compared to the {Standard of care + placebo} group.

- *Rate of patients requiring oxygen supplementation*

To assess the time to hospitalization (all causes and Covid-19 related hospitalization) during the study compared to {Standard of care + placebo} treated group.

- *Time to hospitalization from baseline.*

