4.2. Eligibility Criteria

4.2.1. Inclusion Criteria

A patient will be eligible to participate in this study if ALL the following criteria are met:

1. Adult (≥ 18 years old) men or women, hospitalized or not hospitalized, diagnosed for SARS-CoV-2 infection by PCR or Rapid Antigen tests (approximately 48 hours prior to randomization), with at least one associated risk factor. Considered risk factors are:
 - Age ≥ 65 years
 - Obesity defined as BMI ≥ 30
 - Recent history of uncontrolled High Blood Pressure
 - Treated diabetes (type I or II)
 - History of ischemic cardiovascular disease
2. Symptomatic patients must present at least 1 of the following symptoms at enrollment: fever or perceived fever for more than 24 hours, headache, sore throat, dry cough, fatigue, chest pain or choking sensation (with no associated respiratory distress), myalgia, anosmia, ageusia, or gastro-intestinal symptoms.
3. Patients with pulse oximetry arterial saturation (SpO₂) $\geq 92\%$ on room air at enrolment.
4. Patients with the following hematological and biochemical laboratory parameters obtained within 7 days prior to D0:
 - Hemoglobin > 9.0 g dL⁻¹
 - Absolute Neutrophil Count ≥ 1000 mm⁻³;
 - Platelets $\geq 100,000$ mm⁻³;
 - Creatinine clearance ≥ 50 mL min⁻¹ by the Cockcroft-Gault formula
 - Total serum bilirubin $< 2 \times$ ULN
 - Alkaline phosphatase $< 2 \times$ ULN, AST (SGOT) and ALT (SGPT) $< 3 \times$ ULN;

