8. Patients should be affiliated to a social security regimen (for French sites only).

4.2.2.Exclusion Criteria

Patients who meet any of the following exclusion criteria will be excluded from the study:

1. Patients with moderate or severe acute respiratory failure or requiring non-invasive ventilation or oxygen or with SpO₂ < 92% or tachypnea (respiratory rate ≥ 30 breaths/min).
2. Patients treated with immunosuppressors and/or immunomodulators (cf. Appendix #2).
3. Engrafted patients (organ and/or hematopoietic stem cells).
4. Patients with uncontrolled auto-immune disease.
5. Patients with known or suspected active (i.e. not controlled) bacterial, viral (excluding COVID-19) or fungal infections.
6. Patients with preexisting, severe and not controlled organ failure.
7. History or active malignancy requiring chemotherapy or radiation therapy (excluding 2 years disease free survivor patients).
8. Pregnant or breast-feeding women.
9. Illicit drug or alcohol abuse or dependence that may compromise the patient's safety or adherence to the study protocol.
10. Use of any investigational or non-registered product within 3 months or within 5 half-lives preceding baseline, whichever is longer.
11. Hypersensitivity to ABX464 and/or its excipients.
12. Any condition, which in the opinion of the investigator, could compromise the patient's safety or adherence to the study protocol.

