9.1.2. Definition of study analysis sets

The following datasets will be defined and used for the analyses:

- Enrolled Analysis Set: All patients enrolled in the study will comprise of enrolled analysis set. There will be no safety or efficacy analysis performed on this set.
- Safety Analysis Set: The Safety analysis set will include all the patients randomized in the study and who have received at least one dose of study medication. The safety analysis will be based on the actual treatment received.
- The Full Analysis Set: FAS is defined as all the patients randomized in the study. The efficacy analysis will be based on FAS. The treatment groups will be compared basis the randomized treatment rather than the actual treatment.
- The per protocol (PP) Set: The Per Protocol analysis set will consist of all patients in the FAS without any major protocol deviation (see section 9.1.1). The PP Analysis Set will be used for sensitivity efficacy analyses.

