9.3.3. Analysis of Secondary Efficacy Endpoints

The following secondary endpoints will be analyzed. The analysis will be done on FAS population

- Rate of patients hospitalized
- Percentage of patients reporting each severity rating on a 7-point ordinal scale at each study visit (i.e. Not hospitalized, no limitations on activities; Not hospitalized, limitation on activities; Hospitalized, not requiring supplemental oxygen; Hospitalized, requiring supplemental oxygen; Hospitalized, on non-invasive ventilation or high flow oxygen devices; Hospitalized, on invasive mechanical ventilation or ECMO; Death)
- Change in the ranking on an ordinal scale from baseline to days 7, 14, 21, 28, 48 and at 3 months after the last study drug intake
- % change and AUC over time of oxygen saturation measured by daily pulse oximetry before hospitalization
- Rate of patients with SpO₂ ≤94% and rate of patients with SpO₂ ≤92% at Day 28
- Change from enrolment in inflammatory markers in plasma (i.e. MCP-1, MIP-1 α, G-CSF, IL-1b, IL-2, IL-6, IL-7, IL-10, IL-17, INF γ and TNF α) and in immune phenotype and assessment of cell-activation markers in PBMCs at D14, D28 for hospitalized patients only
- Rate of patients requiring oxygen supplementation
- Time to hospitalization (log rank) from baseline
- Time to assisted ventilation and oxygen supplementation (log rank) from baseline
- Number of days of assisted ventilation
- Number of days of oxygen supplementation
- Number of days at the hospital from admission to discharge ps
- Change from baseline in microRNA-124 levels in total blood (PAXgene®) at D0, D7 and
- AUC and % of change from enrolment in CRP, Troponin I & T and D-dimer levels
- Time to death and mortality rate (all causes, and Covid-19 related)
- Time to improvement of one level in the 7-point ordinal scale
- SARS-CoV-2 virus in nasopharyngeal sample and/or in blood at Day 0, 7 (hospitalized patients), 14, 21, and 28
- Change in SpO₂ values from D0 to D14 in the outpatient's population

In addition, exploratory analysis to assess the radiological findings for patients hospitalized because of Covid-19 infection consequences will be performed.

Central blinded review of the hospitalization discharge CT-Scans for descriptive analysis with regards to the disease severity and outcomes.

Additional details will be elaborated in the Statistical Analysis Plan (SAP).

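### Time to a one-level improvement is assigned to all randomized patients, which can include outpatients who start in the best category and cannot improve

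*Protocol*

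**What the plan says.** Protocol 9.3.3 lists "Time to improvement of one level in the 7-point ordinal scale" among the secondary endpoints and states "The analysis will be done on FAS population". Section 9.1.2 gives the set no baseline restriction: "FAS is defined as all the patients randomized in the study". Section 2.2 fixes the reference point: "To assess the time to an improvement of one category of the 7-point on an ordinal scale from baseline".

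The mildest of the seven categories is "Not hospitalized, no limitations on activities". Section 4.2.1 admits patients "hospitalized or not hospitalized, diagnosed for SARS-CoV-2 infection by PCR or Rapid Antigen tests". Its symptom criterion is conditional ("Symptomatic patients must present at least 1 of the following symptoms at enrollment") and can be met by, for example, headache or anosmia alone. No criterion requires limited activity. Section 4.2.2 excludes patients "requiring non-invasive ventilation or oxygen", so baseline ratings should fall in the three mildest categories. Section 5.2.1 has the scale rated at Day 0, with the best category available.

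Section 9.3.1 promises Kaplan-Meier plots for time-to-event variables. Section 9.3.3 names a log-rank test for time to hospitalization and for time to ventilation or oxygen, but not for this endpoint, and leaves further detail to the SAP. SAP version 5.0, section 4.13, lists the endpoint among those that will not be derived or analysed after the futility stop.

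**The concern.** A patient who starts in the best category cannot be better than baseline at any later visit. Even worsening and then recovering only returns the patient to the starting point. In an analysis of all randomized patients such a patient contributes time at risk and never an event.

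Two things follow. The height of the Kaplan-Meier curve reflects the baseline mix as well as the speed of recovery. And a real difference in recovery speed looks smaller, because as improvable patients leave the risk set, the remainder is increasingly made up of patients who cannot have the event, and this happens sooner in the arm that recovers faster. Category 1 is one of only three that the eligibility criteria leave open at baseline, so the share could be substantial. The documents do not say how large it is.

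**Working it through.** **The plan's own figure.** There is none for this endpoint. The only power figure, 78% at 800 patients (Protocol 9.5), belongs to the primary endpoint. Simulating 84% versus 75%, 533:267, one-sided 2.5%, with a stop at 300 patients when conditional power is at most 10%, gives 78.8% (unpooled variance) or 80.1% (pooled). That figure is essentially reproduced and does not depend on this point.

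**Ceiling (needs no test or effect size).** Let q be the share starting in the best category and F(t) the cumulative improvement among the rest. Over all randomized patients the curve is (1 − q) × F(t), so it cannot exceed 1 − q. For q = 10, 20, 30 and 50% the ceiling is 0.9, 0.8, 0.7 and 0.5. Above q = 50% the median can never be reached. It can also be missed at lower q: with q = 30% and 70% of improvable patients improved by Day 28, the curve stands at 0.7 × 0.7 = 0.49.

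**Dilution of a hazard comparison.** With a constant hazard among improvable patients and S0, S1 the proportions of them not yet improved on placebo and ABX464, the hazard ratio in the whole set at time t is

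HR × [S1 / (q + (1 − q) S1)] ÷ [S0 / (q + (1 − q) S0)].

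Take HR = 1.25 and q = 30%.
- Control hazard 0.08/day, Day 14: S0 = exp(−1.12) = 0.326 and S1 = exp(−1.40) = 0.247. The ratio is 1.25 × 0.522 ÷ 0.617 = 1.06.
- Control hazard 0.08/day, Day 28: S0 = 0.106 and S1 = 0.061. The ratio is 0.78.
- Control hazard 0.01/day, Day 28: S0 = 0.756 and S1 = 0.705. The ratio is 1.22.

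Dilution is therefore strong when most improvable patients recover within the horizon and slight when few do.

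**Power illustration.** Everything here is assumed except 800 patients, 2:1 allocation and the one-sided 2.5% level, which are borrowed from the primary endpoint: true HR 1.25, improvement seen at weekly visits, 28-day horizon, log-rank test, q = 30%.

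| Control hazard per day | Improvable placebo patients improved by Day 28, 1 − exp(−28h) | Power, baseline category 2 or worse | Power, all randomized |
|---|---|---|---|
| 0.08 | 89% | 65% | 21% |
| 0.04 | 67% | 54% | 36% |
| 0.02 | 43% | 40% | 31% |
| 0.01 | 24% | 27% | 24% |

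Repeat runs moved single entries by up to about four points, so the last row shows little or no loss. With q = 10% the pairs are 74% versus 50% at 0.08/day, 66% versus 57% at 0.04/day and 47% versus 45% at 0.02/day.

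**Varying q in a second set-up.** Assume HR 1.3, 70% of improvable placebo patients improved by Day 28, and exact event times. For q = 10, 20, 30 and 50%, power in all randomized patients is about 71, 59, 46 and 26%. The restricted analysis has the same expected events D (548, 487, 425, 305). Its power is Φ(ln 1.3 × √(D × 2/9) − 1.96); for D = 425 this is Φ(0.262 × 9.72 − 1.96) = Φ(0.59) = 72%. Across the four values it is 83, 78, 72 and 58%.

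**The case against.** The strongest objection is status. The trial was stopped for futility and SAP version 5.0 drops this endpoint, so no analysis now planned is affected. That stands, and it is why the point is minor. The SAP shelves the rule without correcting it.

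Second, the protocol is silent rather than explicit. No sentence says that best-category patients stay at risk, and 9.3.3 defers detail to the SAP. Version 4.0 removed the efficacy analyses, so an at-risk rule may have existed in a version not available here. This also stands in part: inclusion follows from the stated population plus the absence of a restriction. But 9.3.3 does restrict other items, limiting inflammatory markers to hospitalized patients and one SpO2 endpoint to outpatients, and it does not restrict this one.

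Third, a reader might infer that the protocol plans a 28-day log-rank or hazard-ratio analysis that loses most of its power. The documents do not support that. They name neither a test, nor a hazard ratio, nor a horizon for this endpoint; the scale is also rated at Day 48 and, for patients who were hospitalized, at three months; and no secondary endpoint is powered. The 65% versus 21% contrast sits at the severe end of the assumed hazards. The ceiling of 1 − q needs none of these assumptions.

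**Conclusion.** The point holds as a minor improvement to a secondary endpoint. As written, the population for time to a one-level improvement can include patients who cannot have the event. This caps cumulative improvement at 1 − q in both arms and dilutes any hazard comparison. The size is not known from the documents: at q = 30% and HR 1.25 the illustrated loss runs from about 44 points of power (0.08/day) to about 3 (0.01/day), and it is smaller at q = 10%. The baseline share, the control hazard, the hazard ratio, the horizon and the test are all assumptions.

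A reader might infer that the trial's main result or reported findings are compromised. They are not: primary power and type I error do not depend on this endpoint, and the current SAP does not report it.

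**What to change.** In Protocol 9.3.3, state that time to a one-level improvement is analysed in Full Analysis Set patients whose baseline rating is category 2 or worse, and report by arm how many patients are left out for starting in category 1.

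The cost is one sentence. The Day 0 rating is already collected. No events are lost, because those removed cannot have one, and selecting on a baseline rating keeps the randomized comparison. The change applies to the protocol's efficacy plan and to any later efficacy report; SAP version 5.0 needs no change while the endpoint stays out of scope. The time horizon and the handling of deaths for this endpoint are separate matters that this sentence does not settle.

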9.4. Clinical laboratory evaluation

Descriptive statistics for laboratory parameters will be computed at each scheduled assessment. If relevant for some parameter, descriptive statistics of change from baseline will also be presented.

In addition, shift tables from baseline will also be presented.

9.5. Determination of Sample Size

For the sample size calculation, the following assumptions will be made:

- Response rate (ABX464): 84 %
- Response rate (placebo): 75 %
- Type 1 error: 2.5% one-sided.
- 2:1 (ABX464 50mg: placebo) study treatment allocation ratio.
- One futility interim analysis after approximately 300 patients complete Day 28 assessment or reach end of study: non-binding futility criterion is a conditional power (calculated under observed effect) $\leq 10\%$.

If the above assumptions hold true, then an initial total sample size of 800 patients will lead to a power of 78%. Sample size re-assessment and potential increase to 1034 patients is described below in section 9.7.

All sample size / power calculations were performed using EAST 6.5.

9.6. Multiplicity adjustment:

Not applicable.

9.7. Interim analysis and sample size reassessment:

One interim analysis is planned after approximately 300 of randomized patients' complete day 28 assessment or reach end of study. Potential early stopping for futility will be based on a boundary defined by conditional power (see details below). It is a non-binding futility approach so that it may be overruled by the DSMB or the Sponsor.

The purposes for the interim analysis are to:

- assess the safety of the study treatment;
- potentially stop the study early for futility;
- re-assess the total sample size and potentially increase it from 800 to 1034 patients.

Interim analysis will be performed without unblinding the sponsor.

Sample size re-assessment will be performed according to rules described in the table below. The scenarios are defined by conditional power for the primary efficacy endpoint calculated under the effect observed at the interim analysis.

Scenario	DSMB Recommendation to Sponsor
Conditional power $\leq 10\%$	Stop study for futility
Conditional Power is between 10% and 80%	Continue study, increase total sample size to 1034
Conditional Power $\geq 80\%$	Continue study with initially planned total sample size 800

If the total sample size is kept to 800, then the final analysis of the primary efficacy endpoint will be performed by a conventional CMH test (with MI handling of missing values) including all data from patients in the FAS and a one-sided significance level of 0.025.

If the total sample size is increased to 1034, then the final analysis of the primary efficacy endpoint will be performed by a weighted test statistic combining

the test statistic Z_1 from the CMH test (with MI handling of missing values) based on primary efficacy endpoint data from n_1 FAS patients included in the interim analysis

and the test statistic Z_2 from the CMH test (with MI handling of missing values) based on primary efficacy endpoint data from FAS patients not included in the interim analysis

using pre-specified weights per the Cui, Hung, Wang (1999) method:

- $w_1 = \sqrt{\frac{n_1}{800}}$
- $w_2 = \sqrt{\frac{800-n_1}{800}}$

as $Z_{final} = w_1 \cdot Z_1 + w_2 \cdot Z_2$ (note that n_1 is planned to be 300 and 800 is the initially planned total sample size). The null hypothesis of equal primary efficacy response probabilities in both study treatment groups will be rejected if $Z_{final} < 1.96$ which corresponds to a one-sided significance level 0.025.

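### The success rule for the 1034-patient trial has its inequality the wrong way round: as printed it rejects a true null hypothesis with probability 0.975, not 0.025

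*Protocol*

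**What the plan says.** Protocol section 9.7 plans one interim analysis after about 300 patients, with three outcomes set by conditional power under the observed effect. At 10% or below, the recommendation is to stop for futility. At 80% or above, the trial continues to 800. Between the two, the recommendation is "Continue study, increase total sample size to 1034".

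For the 800-patient outcome, the final test is a conventional CMH test at one-sided 0.025, and no inequality is printed. For the 1034-patient outcome, the final statistic is Z_final = w1·Z1 + w2·Z2 with Cui-Hung-Wang weights w1 = sqrt(n1/800) and w2 = sqrt((800 − n1)/800). The decision rule is that the hypothesis of no difference in response between the arms "will be rejected if $Z_{final} < 1.96$ which corresponds to a one-sided significance level 0.025".

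Section 9.5 fixes the error rate ("Type 1 error: 2.5% one-sided") and the direction of interest: "Response rate (ABX464): 84"%, "Response rate (placebo): 75"%. Neither section says which arm a positive Z1 or Z2 favours. The current SAP does not repeat the rule: its efficacy section (4.10) is marked not applicable, and the cross-reference to the re-assessment in section 4.12 is broken.

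**The concern.** The two halves of the sentence cannot both be true. A one-sided 0.025 test of a standard normal statistic rejects in one tail, beyond 1.96 or below −1.96. The region below +1.96 is everything except the upper tail.

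This is the only rejection region printed for the extended trial, and it belongs to the primary endpoint of an adaptive design, where protection of the error rate rests on pre-specification. Read literally, a null result is a success. If positive Z favours ABX464, a clear benefit is also a failure. If the intended rule had to be inferred after the data were seen, the pre-specification would have failed at the point where it matters most.

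**Working it through.** **Inputs.** From Protocol 9.5: 84% versus 75%, one-sided 2.5%, "2:1 (ABX464 50mg: placebo) study treatment allocation ratio", total 800 (533 and 267 in section 3.1), futility at conditional power ≤ 10%. From Protocol 9.7: n1 = 300, extension to 1034, upper cut-off 80%, and the weights.

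**1. The protocol's own power figure.** The protocol states that "an initial total sample size of 800 patients will lead to a power of 78"%. The unpooled standard error is sqrt(0.84·0.16/533 + 0.75·0.25/267), and 0.09 divided by it gives a drift of 2.913. With success defined as Z > 1.96:
- without futility, power = Φ(2.913 − 1.96) = 83.0%;
- with futility at conditional power ≤ 10% enforced (bivariate normal, information fraction t = 300/800 = 0.375), power = 77.7%.

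The second figure matches the stated 78%, so the design calculations use an upper-tail rule.

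**2. Null distribution of Z_final.** w1 = sqrt(0.375) = 0.612 and w2 = sqrt(0.625) = 0.791, so w1² + w2² = 1. Under the null, Z_final is N(0,1):
- P(Z_final < 1.96) = 0.975 (as printed)
- P(Z_final > 1.96) = 0.025
- P(Z_final < −1.96) = 0.025

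If positive Z favours ABX464, the inequality is reversed. If negative Z favours ABX464, a minus sign is missing. The printed region has probability 0.975 in both cases.

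**3. When the rule is used.** Conditional power under the observed effect is Φ((Z1/sqrt(t) − 1.96)/sqrt(1 − t)). It equals 10% at Z1 = 0.580 and 80% at Z1 = 1.608, so the extended branch is 0.580 < Z1 < 1.608, measured in favour of ABX464.

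**4. Operating characteristics.** These take positive Z as favouring ABX464, the table as followed and no missing data. The mean of Z1 is drift·sqrt(300/800) and the mean of the extended-stage Z2 is drift·sqrt(734/800). Integrating over Z1:

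| | Null (drift 0) | 84% vs 75% (drift 2.913) |
|---|---|---|
| Extended branch entered | 22.7% | 31.6% |
| Rejects given extended, as printed | 95.2% | 12.0% |
| Rejects given extended, Z_final > 1.96 | 4.8% | 88.0% |
| Rejects through the 800 branch | 1.0% | 53.8% |
| Overall rejection, as printed | 22.6% | 57.6% |
| Overall rejection, corrected | 2.1% | 81.5% |

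The overall rows are branch probability times rejection rate, plus the 800-branch contribution. For example, 0.227·0.952 + 0.010 = 0.226. The 4.8% is conditional on a promising interim result; the unconditional level of the corrected test is 0.025.

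**5. Cross-check with binomial data.** One million simulated trials per scenario, using pooled unstratified Z statistics, gave overall type I error of 22.2% as printed and 2.2% corrected, and power of 60.2% as printed and 83.5% corrected. At 70% versus 75%, a harmful drug, about 5.9% of trials were extended and the printed rule rejected in 99.9% of those.

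**6. The other sign.** If negative Z favours ABX464, the printed rule rejects in almost every extended trial. Overall type I error is then about 23.7% and nominal power about 85.3%, so no power is lost but the error rate is still not controlled.

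**The case against.** The strongest reply is that this is a one-character slip that its own sentence corrects. The 0.025 level stands beside the inequality, section 9.5 repeats it, the method is named, and the stated power fits only an upper-tail rule. That is fair, and the intended rule can be recovered. But recovering it takes inference and a choice of sign that the documents do not make.

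Several limits on the consequences also stand:
- The loss of power, and the rejection of true successes, require that positive Z favours ABX464. The type I error failure does not.
- Only the 1034 branch is affected. The 800 branch states a level without a faulty inequality.
- A trial trending towards harm at the interim falls in the futility row. A harmful final estimate meets the printed rule only after a second-stage reversal or a departure from the table. A null result needs neither.
- The overall figures treat futility as followed, whereas section 9.7 makes it non-binding. If it were overruled and the trial continued to 800, the corrected design would have type I error of 2.5% and the printed one about 23.0%.
- SAP sections 1 and 4.13 record that the DSMB concluded futility on 04 March 2021, that the study was terminated and that the primary endpoint will not be analysed. The rule no longer affects any result.
- The formula was read from a PDF by a program, so a misread character cannot be excluded without looking at the source page.

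None of these makes the printed rule a 0.025 test.

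**Conclusion.** The concern holds. The printed rejection region has null probability 0.975 against a claimed 0.025, under either sign of Z, and no other text in the protocol or current SAP corrects it. With positive Z favouring ABX464 and the conditional-power table followed, overall type I error is about 22.6% instead of 2.1%, and power at 84% versus 75% is about 57.6% instead of 81.5%. These figures assume a normal approximation with unpooled variance, no missing data and no stratification effect; the binomial check moves them by up to about 2.6 percentage points. The error is probably typographical and no longer has a practical consequence for this trial. Because it sits in the pre-specified primary decision rule, it must be fixed in the protocol text.

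**What to change.** In Protocol section 9.7, define the sign and turn the inequality round. For example: Z1 and Z2 are signed so that positive values mean a higher response probability on ABX464, and the null hypothesis is rejected in favour of ABX464 if Z_final > 1.96 (one-sided 0.025). State the same direction for the 800-patient CMH test, so that both branches read alike. First check the inequality against the source PDF page.

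The cost is one line of protocol wording, with no extra patients and no change to the design calculations, which already assume this rule. The current SAP contains no version of the rule to amend. If the efficacy analysis were ever reinstated, the SAP should carry the corrected rule and a working cross-reference in section 4.12.
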